11.2 Definitions of Measurable and Non-Measurable Disease

11.21 Measurable Disease

11.211 A non-nodal lesion is considered measurable if its longest diameter can be accurately measured as ≥ 2.0 cm with chest x-ray, or as ≥ 1.0 cm with CT scan, CT component of a PET/CT, or MRI.

11.212 A superficial non-nodal lesion is measurable if its longest diameter is ≥ 1.0 cm in diameter as assessed using calipers (e.g. skin nodules) or imaging.

11.213 A malignant lymph node is considered measurable if its short axis is ≥ 1.5 cm when assessed by CT scan (CT scan slice thickness recommended to be no greater than 5 mm).

NOTE: Tumor lesions in a previously irradiated area are considered measurable disease under the following conditions:

- Tumor lesions in a previously irradiated area are considered target lesions only if they have progressed after XRT and prior to start this investigational protocol.

11.22 Non-Measurable Disease

11.221 All other lesions (or sites of disease) are considered non-measurable disease, including pathological nodes (those with a short axis ≥ 1.0 to < 1.5 cm). Bone lesions, leptomeningeal disease, ascites, pleural/pericardial effusions, lymphangitis cutis/pulmonis, inflammatory breast disease, and abdominal masses (not followed by CT or MRI), are considered as non-measurable as well.

Note: ‘Cystic lesions’ thought to represent cystic metastases can be considered as measurable lesions, if they meet the definition of measurability described above. However, if non-cystic lesions are present in the same patient, these are preferred for selection as target lesions. In addition, lymph nodes that have a short axis < 1.0 cm are considered non-pathological (i.e., normal) and should not be recorded or followed.

11.3 Guidelines for Evaluation of Measurable Disease

11.31 Measurement Methods:

- All measurements should be recorded in metric notation (i.e., decimal fractions of centimeters) using a ruler or calipers.
- The same method of assessment and the same technique must be used to characterize each identified and reported lesion at baseline and during follow-up.

up. For patients having only lesions measuring at least 1 cm to less than 2 cm must use CT imaging for both pre- and post-treatment tumor assessments.

- Imaging-based evaluation is preferred to evaluation by clinical examination when both methods have been used at the same evaluation to assess the antitumor effect of a treatment.

11.32 Acceptable Modalities for Measurable Disease:

- Conventional CT and MRI: This guideline has defined measurability of lesions on CT scan based on the assumption that CT slice thickness is 5 mm or less. If CT scans have slice thickness greater than 5 mm, the minimum size for a measurable lesion should be twice the slice thickness.
- As with CT, if an MRI is performed, the technical specifications of the scanning sequences used should be optimized for the evaluation of the type and site of disease. The lesions should be measured on the same pulse sequence. Ideally, the same type of scanner should be used and the image acquisition protocol should be followed as closely as possible to prior scans. Body scans should be performed with breath-hold scanning techniques, if possible.
- FDG-PET: FDG-PET scanning is allowed to complement CT scanning in assessment of progressive disease [PD] and particularly possible 'new' disease. A 'positive' FDG-PET scanned lesion is defined as one which is FDG avid with an uptake greater than twice that of the surrounding tissue on the attenuation corrected image; otherwise, an FDG-PET scanned lesion is considered 'negative.' New lesions on the basis of FDG-PET imaging can be identified according to the following algorithm:
 - a. Negative FDG-PET at baseline with a positive FDG-PET at follow-up is a sign of PD based on a new lesion.
 - b. No FDG-PET at baseline and a positive FDG-PET at follow-up:
 - i. If the positive FDG-PET at follow-up corresponds to a new site of disease confirmed by CT, this is PD.
 - ii. If the positive FDG-PET at follow-up is not confirmed as a new site of disease on CT at the same evaluation, additional follow-up CT scans (i.e., additional follow-up scans 8 weeks after the prior CT) are needed to determine if there is truly progression occurring at that site. In this situation, the date of PD will be the date of the initial abnormal PDG-PET scan.
 - iii. If the positive FDG-PET at follow-up corresponds to a pre-existing site of disease on CT that is not progressing on the basis of the anatomic images, it is not classified as PD.

11.33 Measurement at Follow-up Evaluation:

- A subsequent scan must be obtained 8 weeks following initial documentation of an objective status of either complete response (CR) or partial response (PR).
- In the case of stable disease (SD), follow-up measurements must have met the SD criteria at least once after study entry at a minimum interval of 8 weeks (see Section 11.44).
- The cytological confirmation of the neoplastic origin of any effusion that appears or worsens during treatment when the measurable tumor has met criteria for response or stable disease is mandatory to differentiate between response or stable disease (an effusion may be a side effect of the treatment) and progressive disease.
- Cytologic and histologic techniques can be used to differentiate between PR and CR in rare cases (e.g., residual lesions in tumor types such as germ cell tumors, where known residual benign tumors can remain.)

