11.0 Treatment Evaluation Using RECIST Guideline

Response and progression will be evaluated in this study using the new international criteria proposed by the revised Response Evaluation Criteria in Solid Tumors (RECIST) guidelines (version 1.1 (Eisenhauer EA, Therasse P, Bogaert J, *et al.*, 2009)). Changes in the largest diameter (unidimensional measurement) of the tumor lesions and the short axis measurements in the case of lymph nodes are used in the RECIST guideline.

11.1 Schedule of Evaluations: For the purposes of this study, patients should be reevaluated every 8 weeks.

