13.0 Treatment/Follow-up Decision at Evaluation of Patient

13.1 Patients who are CR, PR, or SD will continue treatment per protocol. Patients who are CR, PR, or SD at time of their reassessment and **have not** experienced intolerable toxicity will be allowed to continue protocol treatment at the same dose level until PD or maximum of 3 years whichever is earlier.

Those patients who are CR, PR, or SD but **have** experienced unacceptable toxicity may be eligible for retreatment at a lower dose until PD or maximum of 3 years whichever is earlier, at discretion of treating physician (see Section 8.0).

13.2 Patients who develop PD while receiving therapy will go to the event-monitoring phase. Treatment decision during event-monitoring phase is at the discretion of the treating physician.

13.3 Patients who go off protocol treatment for reasons other than PD will go to the event-monitoring phase per Section 18.0. Treatment decision during event-monitoring phase is at the discretion of the treating physician.

13.4 If a patient enrolled to Phase I dose escalation part of the study fails to complete the initial course of therapy (defined as drug administration \leq 75% of expected cycle 1 total dose) for reasons other than dose-limiting toxicity defined adverse events, the patient will be regarded as uninformative in regard to the primary study goal and an additional patient will be enrolled at the current dose level

13.5 A patient is deemed *ineligible* if after registration, it is determined that at the time of registration, the patient did not satisfy each and every eligibility criteria for study entry. The patient may continue treatment off-protocol at the discretion of the physician as long as there are no safety concerns, and the patient was properly registered. The patient will go directly to the event-monitoring phase of the study (or off study, if applicable).

- If the patient received treatment, all data up until the point of confirmation of ineligibility must be submitted. Event monitoring will be required per Section 18.0 of the protocol.
- If the patient never received treatment, on-study material must be submitted. Event monitoring will be required per Section 18.0 of the protocol.

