16.42 Decision Rule

The largest success proportion (proportion of evaluable patients with CR/PR) where the proposed treatment regimen would be considered ineffective in this population is 23% (Von Hoff et. al., 2013²⁹ and Conroy et. al., 2011³⁰), and the smallest success proportion that would warrant subsequent studies with the proposed regimen in this patient population is 45%.

Evaluable patients for the primary endpoint are defined as patients with HRD encompassing BRCA1, BRCA2, and PALB2 deleterious mutations (germline and somatic), consented, eligible, and received any protocol treatment. The following two-stage Simon's design and an interim analysis with relaxed probability of stopping for futility uses a minimum of 11 and a maximum of 21 patients to test the null hypothesis that the true success proportion in a given patient population is at most 23%. The current design assumes a one-sided alpha level 0.1 and 80% power. The above power calculation was done using Simon's like design with relaxed futility stopping (Ivanova A.) and assumes a one-sided alpha level 0.1, 80% power, and lower and upper bound for the probability of stable disease (SD) to be 0.1 and 0.2, respectively.

16.421 STAGE 1

Among first 11 patients enrolled into study, if 2 or fewer patients with CR/PR/SD are observed ≤ 16 weeks after registration, we will consider this regimen ineffective in this patient population and terminate the study. Otherwise, if at least 3 patients with CR/PR/SD are observed ≤ 32 weeks after registration, we will proceed to Stage 2 and continue accrual.

16.422 STAGE 2

The regimen will be considered ineffective if either enrollment is

discontinued after stage 1 or if 7 or fewer patients with CR/PR are observed in the first 21 evaluable patients. This regimen will be considered promising if 8 or more patients with CR/PR are observed in the first 21 evaluable patients.

16.423 Over Accrual

If more than the target number of patients are accrued, the additional patients will not be used to evaluate the stopping rule or used in any decision-making process. Analyses involving over accrued patients are discussed in Section 16.5.

16.424 Operating characteristics

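### The stage 1 futility count in 16.421 does not exclude patients whose stable disease has progressed before the look, which weakens an already relaxed rule by an amount the documents do not fix

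*Combined protocol and SAP*

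**What the plan says.** Section 16.42 sets the null response rate as the largest that "would be considered ineffective in this population is 23"%, and states that "the smallest success proportion that would warrant subsequent studies with the proposed regimen in this patient population is 45"%. It adds: "The current design assumes a one-sided alpha level 0.1 and 80% power". The design "uses a minimum of 11 and a maximum of 21 patients to test the null hypothesis". The probability of SD is bounded between 0.1 and 0.2.

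Section 16.421 stops accrual "if 2 or fewer patients with CR/PR/SD are observed ≤ 16 weeks after registration" among the first 11 patients. The continue clause in the same paragraph needs at least 3 such patients but gives a 32-week window. The final decision (16.422) uses CR/PR only: 8 or more of 21.

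On SD, section 11.33 says that "follow-up measurements must have met the SD criteria at least once after study entry at a minimum interval of 8 weeks". Section 11.1 says "patients should be reevaluated every 8 weeks". Section 13.2 says "Patients who develop PD while receiving therapy will go to the event-monitoring phase".

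Section 16.424 tabulates the probability of stopping at stage 1, from 12.12% at a true rate of 0.23 down to 0.58% at 0.45.

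**The concern.** The endpoint is CR/PR within 32 weeks of registration. Counting SD at an earlier look makes sense because a stable patient may still respond. A patient who was stable at week 8 and has since progressed no longer has that prospect on protocol treatment, so counting that patient as evidence for continuing carries no useful information.

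The wording of 16.421 is cumulative (status seen at some time up to a limit), 11.33 is satisfied by one qualifying assessment, and no section takes a later progressor out of the count. Phase Ib is handled differently: disease control there (16.11, 16.32) requires the status to last at least 24 weeks. Section 16.421 has no such condition.

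At stake is early stopping. Patients with untreated metastatic disease and BRCA1/2 or PALB2 mutations could go on being enrolled to an ineffective regimen. In addition, two statisticians could reach opposite stop or continue decisions from the same 11 patients.

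**Working it through.** **Inputs.** From 16.42 to 16.422: p0 = 0.23, p1 = 0.45, n1 = 11, N = 21, stop if 2 or fewer counted, success if 8 or more CR/PR, SD probability s between 0.1 and 0.2. Assumed, because the documents do not give it: e, the share with SD at week 8 and progression before the look.

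**Formula.** If q is the probability that a patient is counted at stage 1, then

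P(stop) = (1−q)^11 + 11·q·(1−q)^10 + 55·q²·(1−q)^9.

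Alpha and power come from exact trinomial enumeration of stage 1 (CR/PR, SD, neither), followed by a binomial for the 10 stage 2 patients.

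**Step 1: reproduce the plan's table.** With q = p + s:

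| True rate | Exact P(stop), s = 0.1 to 0.2 | 16.424 |
|---|---|---|
| 0.23 | 24.1% to 8.4% | 12.12% |
| 0.30 | 11.9% to 3.3% | 9.67% |
| 0.35 | 6.5% to 1.5% | 5.44% |
| 0.40 | 3.3% to 0.6% | 1.20% |
| 0.45 | 1.5% to 0.2% | 0.58% |

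At 0.23 with s = 0.1, q = 0.33: 0.0122 + 0.0662 + 0.1630 = 0.2413. With s = 0.2, q = 0.43: 0.0021 + 0.0171 + 0.0646 = 0.0838.

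The probability of declaring the regimen promising is 8.65% to 8.74% at 0.23 (stated 8.34%, simulation standard error √(0.0834 × 0.9166 / 10,000) ≈ 0.28 points) and 80.0% to 80.3% at 0.45 (stated 79.69%). The table is therefore consistent with the stated SD bounds. No single s gives all five stopping values (implied s: 0.168, 0.118, 0.114, 0.162, 0.151).

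**Step 2: reading A, the planned 0.1 to 0.2 already includes SD that later progresses.** As written, P(stop) at 0.23 is 24.1% to 8.4%. Excluding progressors lowers the counted SD share and raises stopping. If half of s = 0.2 has progressed, q falls from 0.43 to 0.33 and P(stop) rises from 8.4% to 24.1%. The ceiling, with no SD counted at all (q = 0.23), is 51.9%.

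**Step 3: reading B, the planned 0.1 to 0.2 means SD without progression.** As written, q = 0.23 + s + e:

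| e (assumed) | s = 0.1 | s = 0.2 |
|---|---|---|
| 0 (progressors excluded) | 24.1% | 8.4% |
| 0.1 | 8.4% | 2.1% |
| 0.2 | 2.1% | 0.3% |
| 0.3 | 0.3% | 0.02% |

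**Step 4: error rates and patients.** Alpha runs from 8.38% (no SD counted) to 8.78% (no interim stopping). Power runs from 78.82% to 80.29% over the same extremes.

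Expected N at the null is 11 + 10 × (1 − P(stop)): 18.6 at 24.1%, 19.8 at the tabulated 12.12%, 20.2 at 8.4% and 20.8 at 2.1%. Under reading B the excess from counting progressors is 10 × the difference in P(stop). It runs from 10 × (0.0838 − 0.0206) = 0.6 patients (s = 0.2, e = 0.1) to 10 × (0.2413 − 0.0032) = 2.4 patients (s = 0.1, e = 0.3).

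**Step 5: timing.** The limit runs from registration, but treatment may start up to 21 days later (6.44), and scans precede cycle 3 and later odd cycles (4.0). With 28-day cycles the second scan is due about 16 weeks after treatment starts, so it can fall at about week 19 after registration. For such a patient the week-8 scan may be the only one inside a 16-week limit.

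**The case against.** The strongest reply is that the text is silent rather than wrong. Section 11.33 sets a minimum interval before SD can be called; it does not say that SD survives later progression. Section 11.44 defines objective status evaluation by evaluation, so reading 16.421 as status at the look is not excluded. That stands: the literal reading is the cumulative one, but no rule states that progressors count.

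A reader might also infer that counting progressors is why the rule rarely stops an ineffective regimen. The documents do not support that. The plan says openly that futility stopping is relaxed (16.4, 16.42), states its SD assumption and tabulates 12.12%. The low figure comes mainly from counting SD at all with a cut-off of 2 of 11. With progressors excluded and s = 0.1 to 0.2, stopping is still only 8.4% to 24.1%.

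Nor can one conclude that true stopping is well below the tabulated figure. The values from 8.4% down to 0.02% in step 3 require reading B plus an assumed share on top of the planned SD bound. Under reading A the rule as written brackets 12.12%. The veliparib experience in section 1.7 (15% response, 46% SD, 27% for 6-month time to progression) is only suggestive: 13 refractory patients, another regimen, and no information on progression between weeks 8 and 16.

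Finally, because the second scan can come after the limit, progression is not always known at the look. The consequence is also bounded: the final decision uses CR/PR alone, and the DSMB reviews the study every 6 months. These points limit the weight of the concern but do not remove the gap.

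**Conclusion.** The point holds in a limited form. As worded, 16.421 with 11.33 lets a patient with week-8 SD who has progressed before the look count toward the 3 of 11. Excluding such patients can only raise the chance of stopping.

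How much depends on two things the documents leave open: whether the 0.1 to 0.2 SD probability includes these patients, and how many there are. At a true rate of 0.23, illustrative effects are 8.4% rising to 24.1% with the fix (reading A, half of SD 0.2 progressed), or 24.1% to 8.4% reduced to 8.4% to 2.1% by the present wording (reading B, an assumed extra 10%).

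The validity of the final test is not in question: alpha stays at about 8.4% to 8.8% and power at 78.8% to 80.3%. The cost of leaving the wording as it is falls on patients: up to 10 more treated when the regimen is ineffective, or about 0.6 to 2.4 in expectation at the null under reading B with an assumed share of 0.1 to 0.3. This is a cheap improvement, not a flaw that undermines the design.

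**What to change.** Amend 16.421 as follows:

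- Count a patient toward the 3 of 11 only if CR/PR has been observed, or if the latest assessment available at the look is SD with no progression recorded. State that SD followed by progression before the look is a failure at the interim.
- Define the look by the second scheduled scan or by a stated window that allows for the treatment-start lag of up to 21 days.
- Use one window in both the stop and the continue clause (now 16 and 32 weeks).
- State that the 0.1 to 0.2 SD probability uses this same definition, and rerun the 16.424 table.

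Section 11.33 can stay as it is for response reporting. No new data are needed; the work is a short text edit and a rerun of the operating characteristics. The statistical price is a power loss of about 0.3 points or less when SD without progression is 0.1 to 0.2 (at most 80.29% to 80.01%), and about 1.5 points if there is none (80.29% to 78.82%).

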11.4 Measurement of Effect

11.41 Target Lesions & Target Lymph Nodes

- Measurable lesions (as defined in Section 11.21) up to a maximum of 5 lesions, representative of all involved organs, should be identified as “Target Lesions” and recorded and measured at baseline. These lesions can be non-nodal or nodal (as defined in 11.21), where no more than 2 lesions are from the same organ and no more than 2 malignant nodal lesions are selected.

Note: If fewer than 5 target lesions and target lymph nodes are identified (as there often will be), there is no reason to perform additional studies beyond those specified in the protocol to discover new lesions.

- Target lesions and target lymph nodes should be selected on the basis of their size, be representative of all involved sites of disease, but in addition should be those that lend themselves to reproducible repeated measurements. It may be the case that, on occasion, the largest lesion (or malignant lymph node) does not lend itself to reproducible measurements in which circumstance the next largest lesion (or malignant lymph node) which can be measured reproducibly should be selected.
- Baseline Sum of Dimensions (BSD): A sum of the longest diameter for all target lesions plus the sum of the short axis of all the target lymph nodes will be calculated and reported as the baseline sum of dimensions (BSD). The BSD will be used as reference to further characterize any objective tumor response in the measurable dimension of the disease.
- Post-Baseline Sum of the Dimensions (PBSD): A sum of the longest diameter for all target lesions plus the sum of the short axis of all the target lymph nodes will be calculated and reported as the post-baseline sum of dimensions

(PBSD). If the radiologist is able to provide an actual measure for the target lesion (or target lymph node), that should be recorded, even if it is below 0.5 cm. If the target lesion (or target lymph node) is believed to be present and is faintly seen but too small to measure, a default value of 0.5 cm should be assigned. If it is the opinion of the radiologist that the target lesion or target lymph node has likely disappeared, the measurement should be recorded as 0 cm.

- The minimum sum of the dimensions (MSD) is the minimum of the BSD and the PBSD.

11.42 Non-Target Lesions & Non-Target Lymph Nodes

Non-measurable sites of disease (Section 11.22) are classified as non-target lesions or non-target lymph nodes and should also be recorded at baseline. These lesions and lymph nodes should be followed in accord with 11.433.

11.43 Response Criteria

11.431 All target lesions and target lymph nodes followed by CT/MRI/PET-CT/Chest X-ray/physical examination must be measured on re-evaluation at evaluation times specified in Section 11.1. Specifically, a change in objective status to either a PR or CR cannot be done without re-measuring target lesions and target lymph nodes.

Note: Non-target lesions and non-target lymph nodes should be evaluated at each assessment, especially in the case of first response or confirmation of response. In selected circumstances, certain non-target organs may be evaluated less frequently. For example, bone scans may need to be repeated only when complete response is identified in target disease or when progression in bone is suspected.

11.432 Evaluation of Target Lesions

- Complete Response (CR): All of the following must be true:
 - Disappearance of all target lesions.
 - Each target lymph node must have reduction in short axis to <1.0 cm.

- Partial Response (PR):

At least a 30% decrease in PBSD (sum of the longest diameter for all target lesions plus the sum of the short axis of all the target lymph nodes at current evaluation) taking as reference the BSD (*see* Section 11.41).

- Progression (PD): At least one of the following must be true:
 - a. At least one new malignant lesion, which also includes any lymph node that was normal at baseline (< 1.0 cm short axis) and increased to \geq 1.0 cm short axis during follow-up.
 - b. At least a 20% increase in PBSD (sum of the longest diameter for all target lesions plus the sum of the short axis of all the target lymph nodes at current evaluation) taking as reference the MSD (Section 11.41). In addition, the PBSD must also demonstrate an absolute increase of at least 0.5 cm from the MSD.
 - c. See Section 11.32 for details in regards to the requirements for PD via FDG-PET imaging.
- Stable Disease (SD): Neither sufficient shrinkage to qualify for PR, nor sufficient increase to qualify for PD taking as reference the MSD.

11.433 Evaluation of Non-Target Lesions & Non-target Lymph Nodes

- Complete Response (CR): All of the following must be true:
 - a. Disappearance of all non-target lesions.
 - b. Each non-target lymph node must have a reduction in short axis to < 1.0 cm.
- Non-CR/Non-PD: Persistence of one or more non-target lesions or non-target lymph nodes.
- Progression (PD): At least one of the following must be true:
 - a. At least one new malignant lesion, which also includes any lymph node that was normal at baseline (< 1.0 cm short axis) and increased to \geq 1.0 cm short axis during follow-up.

- b. Unequivocal progression of existing non-target lesions and non-target lymph nodes. (NOTE: Unequivocal progression should not normally trump target lesion and target lymph node status. It must be representative of overall disease status change.)
- c. See Section 11.32 for details in regards to the requirements for PD via FDG-PET imaging.

